12NOV2018	
 Cover Page: Updated address for Gala Menlo Park Office Synopsis: Revised number of clinical sites from 5 to 7 Throughout Document: Replaced Gala Airway Treatment (GATS) with RheOx to reflect trademarked device name and minor punctuation/page formatting corrections Schedule of Events Table 7.1: Changed Follow-up CT scan from 3 months to 6 months post-bronchoscopy #2; updated sections 7.2.7 and 7.2.8 accordingly. Removed 'phone call' from Visit #5 in table header to clarify the visit is in-office; this is consistent with section 7.2.5 and Figure 7.1. Changed the time period for the daily diary from entire study period (5 years) to only the first year.
31JAN2019	
 Section 7.2.4 Visit 4/Bronchoscopy #2 added CT scan Table 7.1 Schedule of Events: Added CT at Visit 4 prior to Bronchoscopy #2; removed Induced Sputum from Visit 2/Bronchoscopy #1 and Visit 4/Bronchoscopy #2 and moved superscripts to individual activities for additional clarity
19APR2019	
 Synopsis: Revised number of clinical sites from 7 to 10

PROTOCOL REVISION HISTORY	
Revision Date	DESCRIPTION
	
 • Synopsis: Revised number of patients from 15 to 30 • Synopsis: Revised Other (tertiary) endpoints to include the Insomnia Sleep Index (ISI) and cough count • Section 3.2.3 was updated to include the Insomnia Sleep Index (ISI) and cough count • Section 7.2 clarified wording regarding rescheduling of follow-up visits due to COPD exacerbations • Section 7.4 schedule of events added visit windows, ISI and selected, optional polysomnography, cough counting monitor, and clarified wording regarding rescheduling of follow up visits due to COPD exacerbations • Section 10.2 added urinary retention to minor complications associated with anesthesia • References: added reference 21

STUDY ACKNOWLEDGMENT

Investigator's Statement:

I have read and understand Protocol No. CS003 and agree to conduct the study as outlined herein.

Investigator's Name (please print)

Investigator's Title

Investigator's Signature

Date

Sponsor Signature, Protocol Approval:

This study protocol, Protocol No. CS003, has been reviewed and approved by Gala Therapeutics, Inc., in accordance with Company policy and procedures and the US FDA, as warranted, under IDE requirements per 21 CFR part 812.

For: Gala Therapeutics, Inc.
[name]
[name]

Name (please print)

Study Sponsor	Gala Therapeutics, Inc. Menlo Park, CA USA
Study Device	RheOx™
Design	Prospective, single-arm feasibility study
Objective	Primary: To assess the safety of the RheOx in patients with chronic bronchitis Secondary: To assess the clinical utility of the RheOx in patients with chronic bronchitis
Study Population	The study will treat up to 30 adult patients with chronic bronchitis at up to 10 clinical study sites in the United States Gala will conduct an interim safety analysis after 5 subjects complete the second RheOx procedure to assess the safety profile of the device and procedure and ensure it is safe to continue the study.
Study Period	Subjects receive treatment in the right lung first, followed by treatment of the left lung approximately 4-weeks later. The follow-up period will extend to 5 years following treatment of the second lung. Study follow-up visits will occur at 6-months, 12-months, 2, 3, 4 and 5 years after the second treatment.
Outcome Measures	The primary outcome of the study is safety. The primary safety analysis will be the incidence of serious adverse events of interest through 12 months defined as the following; 
• Death• COPD exacerbation, as defined as an acute worsening in respiratory symptoms requiring additional therapy, that requires a hospital stay of greater than 24 hours• Pneumothorax within 2 days of either Gala Treatment procedure• Pneumonia within 7 days of either Gala Treatment procedure, as defined as an increase in respiratory symptoms, fever, sputum production and or purulence with radiographic confirmation• Respiratory Failure as defined as a requirement for mechanical ventilatory support for > 24 hours• Arrhythmia requiring intervention or sustained (\geq 30 seconds) ventricular tachycardia

The secondary outcome measures of clinical utility will be assessed by;

- The change from baseline at 6 and 12 months in St. George's Respiratory Questionnaire (SGRQ)
- The change from baseline at 6 and 12 months in COPD Assessment Test (CAT)

Hospitalization rates (not including the planned bronchoscopy procedures) from discharge from the initial RheOx Bronchial Rheoplasty procedure (Visit 2) through 12 months

Other (tertiary) endpoints

Other, tertiary and exploratory endpoints will also be assessed including changes from baseline to follow-up in:

- Responder rates utilizing established clinically meaningful thresholds for SGRQ (4 points)¹⁷ and CAT (2 points)¹⁶
- Change in other QOL measures including CASA-Q and EXACT-PRO
- Change in lung function as measured by FEV₁ and FVC
- Change in sleep patterns as assessed by the Insomnia Sleep Index (ISI)
- Change in cough count as assessed by a cough counting monitor
- Mucin concentrations (MUC5AC, MUC5B) from induced sputum samples
- Quantitative High Resolution CT Scan (HRCT) metrics including airway volume, total airway count, and lobar volumes
- Device performance

In addition to the endpoints described above, additional safety analyses in support of the primary study outcome and to assess the totality of safety profile of RheOx, will be conducted.

Adverse events reported from the day of the index procedure through completion or termination of the study will be assessed. AEs and SAEs will be summarized using a standard medical coding dictionary (MedDRA). AEs and SAEs will be also analyzed by severity, relatedness to the device and/or procedure and within discrete time periods in relation to the index procedure.

COPD exacerbations will also be analyzed by severity (mild, moderate, and severe) based on commonly accepted clinical definitions as defined in GOLD 2018 Report¹⁸.

Statistical Considerations

As this is a feasibility study, endpoints will not be powered for statistical significance. Descriptive statistics will be utilized to summarize and report on data for all subject and outcome variables.

Categorical data (e.g., age, gender) will be reported in frequency distributions. Certain dichotomous data (e.g., Adverse Events) will also be presented as rates. Continuous data (e.g., age, FEV₁) will be

summarized using mean, standard deviations, medians, minimums, maximums, and interquartile ranges.

All patients that enter the procedure room for the index RheOx Bronchial Rheoplasty procedure (Visit 2) will be included in the analysis.

Additional subgroup and other multivariable analyses may be performed including examination of the association between subject risk factors (e.g., age, gender) and trial outcomes, and the potential contributions of these factors.

LIST OF ABBREVIATIONS

6MWT	Six Minute Walk Test
AE	Adverse Event
ARDS	Acute Respiratory Distress Syndrome
BAL	Bronchoalveolar lavage
CASA-Q	Cough and Sputum Assessment Questionnaire
CAT	COPD Assessment Test
CBC	Complete Blood Count
CIP	Clinical Investigational Plan
COPD	Chronic Obstructive Pulmonary Disease
CRF	Case Report Form
CT scan	Computed Tomography scan; also referred to as CAT scan
EC	Ethics Committee
EDC	Electronic Data Capture (electronic database)
EKG	Electrocardiogram; also referred to as ECG
EXACT-PRO	EXAcerbations of Chronic pulmonary disease Tool (EXACT) Patient Reported Outcomes
FEV ₁	Forced Expiratory Volume in 1 Second
FVC	Forced Vital Capacity
FDA	Food and Drug Administration
GCP	Good Clinical Practice
GLP	Good Laboratory Practice
HIPAA	Health Insurance Portability and Accountability Act
HHS	Depart of Health and Human Services
ICF	Informed Consent Form
ICH	International Conference on Harmonization
IRB	Institutional Review Board
IRE	Irreversible Electroporation
ISI	Insomnia Sleep Index
MCID	Meaningful Clinically Important Difference
mMRC	Modified Medical Research Council Dyspnea Scale
MRI	Magnetic Resonance Imaging

PFT	Pulmonary Function Test(s)
PI	Principal Investigator
RF	Radiofrequency
RFE	Radiofrequency Energy
SAE	Serious Adverse Event
SGRQ	St. George Respiratory Questionnaire
Tx	Gala Bronchoscopy Treatment
UADE	Unanticipated Adverse Device Effect

DEFINITIONS

Adverse Event (AE): any untoward medical occurrence, unintended disease or injury, or untoward clinical signs (including abnormal laboratory findings) in subjects, user or other persons, whether or not related to the investigational medical device [Reference ISO 14155:2011]

COPD Exacerbation: An acute worsening in respiratory symptoms that requires additional treatment

Mild: Treated with short acting bronchodilators only (SABDs)

Moderate: Treated with SABDs plus antibiotics and/or oral corticosteroids

Severe: Requires hospitalization and or visits to the emergency room. Severe exacerbations may also be associated with acute respiratory failure

Chronic Bronchitis: One form of COPD defined by GOLD guidelines and characterized by chronic productive cough for three months in each of two successive years in a patient in whom other causes of productive cough have been excluded

Serious Adverse Event (SAE): an adverse event that a) led to death, b) lead to serious deterioration in the health of the subject that either resulted in 1) a life-threatening illness or injury, or 2) a permanent impairment of a body structure or a body function, or 3) in-patient or prolonged hospitalization, or 4) medical or surgical intervention to prevent life-threatening illness or injury or permanent impairment to a body structure or a body function, or c) led to fetal distress, fetal death or a congenital abnormality or birth defect [Reference ISO 14155:2011]

Unanticipated Adverse Device Effect (UADE): any serious adverse effect on health or safety or any life-threatening problem or death cause by, or associated with, a device, if that effect, problem or death was not previously identified in nature, severity or degree of incidence in the investigational plan [Reference 21 CFR 812.3(s)]

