7.2.4 Visit #4. Bronchoscopy #2 / Treatment Session #2

Subjects are scheduled for follow-up 3-6 weeks following Bronchoscopy #1. Pre-operative procedures (e.g. CT Scan, physical exam, CBC) are completed in accordance with the Schedule of Events table prior to the bronchoscopy. Any observed adverse events are reported accordingly. If the subject has experienced any complications that preclude continued participation in the study, then additional treatment is halted.

Upon successful completion of the pre-operative procedures, the subject undergoes a bronchoscopy procedure in accordance with standard institutional protocol. Anesthesia is administered. The airways are visualized, and BAL completed. The RheOx Bronchial Rheoplasty is administered to the target sites in the left side lung in accordance with the instructions for use. The clinical investigator ensures FiO₂ does not exceed 40% during energy delivery. Prior to the initiation of energy delivery and during at least one energy delivery a 6 second 3 lead EKG strip is recorded. An EKG rhythm strip from anesthesia monitoring is adequate.

The subject is recovered in accordance with standard institutional procedures and observed overnight at the discretion of the study investigator. The subject is then discharged at the investigator's discretion. Any observed adverse events are reported accordingly.

Note: Bronchoscopy #2 may be delayed or halted at the investigator's discretion if the patient has an active respiratory infection (e.g., common cold, pneumonia, MAI), COPD exacerbation since treatment session #1 or any other significant clinical symptom that may compromise the procedure.

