Additional Notes on Schedule of Events:

Note: If Bronchoscopy #2 cannot be completed the subject should continue follow-up at 3 months, 6 months, 12 months and annually through 5 years following Bronchoscopy #1 (i.e., last treatment session).

Note: If the subject experiences a COPD exacerbation or other change in functional status within 6 weeks of any scheduled follow-up visit, the investigator should consider rescheduling study follow-up visits based on his or her best medical judgement to allow for an accurate assessment of the patient's stable condition once the subjects symptoms have returned to normal. It is recommended that subjects return to clinical baseline for a minimum of two-weeks prior to undergoing study specific follow-up testing.

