7.6.2 Interim Safety Analysis

In addition to the study stopping rules, an interim safety analysis will be conducted after 5 subjects complete the second treatment (Visit 4) to ensure it is safe to continue study treatments. Enrollments and planned study visits/treatments should continue per the study protocol while the interim analysis is being conducted. The interim analysis will consist of a review of all AE and SAE data collected in the study at that point including an assessment of device and procedure relatedness. The data will be reviewed by the study medical monitor and a subcommittee of three Gala Therapeutics Scientific Advisory Board members, composed of experts in chronic bronchitis and interventional bronchoscopy procedures to ensure it is safe to continue the study. Patient demographics and procedural characteristics will also be included in the review. The review should confirm that the safety profile of the study is consistent with expectations set forth at the start of the study.

Recommendations may include:

1. Continue the study without modification
2. Continue the study with modification or
3. Terminate the study

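### The only scheduled aggregate safety review waits for five completed second treatments, so complications that halt or delay the second treatment without meeting a stopping rule postpone it

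*Protocol*

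**What the plan says.** The synopsis (Study Population) sets the trigger: "Gala will conduct an interim safety analysis after 5 subjects complete the second RheOx procedure". Protocol 7.6.2 uses the same one: five subjects who have completed the second treatment. No other trigger is given, whether by first treatments, calendar time or cumulative events. The SAP describes no interim analysis.

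Section 7.2.4 sets out how a subject can miss or postpone the second treatment:

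- "If the subject has experienced any complications that preclude continued participation in the study, then additional treatment is halted".
- "Bronchoscopy #2 may be delayed or halted at the investigator's discretion", the listed reasons being an active respiratory infection, an exacerbation since the first session, or another significant symptom.

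Such subjects stay in the study. The notes to Table 7.1 say: "If Bronchoscopy #2 cannot be completed the subject should continue follow-up". They do not count toward the five unless the second treatment is eventually completed.

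Accrual does not wait. Section 7.6.2 says: "Enrollments and planned study visits/treatments should continue per the study protocol while the interim analysis is being conducted". Once the review is triggered, its content is complete: "The interim analysis will consist of a review of all AE and SAE data collected in the study at that point".

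Three other safeguards operate. Section 7.6.1 halts enrollment and treatment on five kinds of event and requires a review before enrollment resumes. Section 10.1.2 sends every SAE to the sponsor within 24 hours. Section 10.1.1 has the medical monitor follow AEs regularly, without a stated schedule or criteria.

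**The concern.** The review exists to judge whether treatment can safely continue, and section 11.1 cites it as one of the study's protections. Its timing depends on the outcome it judges. If first procedures go smoothly, five subjects reach Visit 4 quickly. If first procedures often lead to infections or exacerbations that stop or postpone the second, the count moves slowly and more subjects have a first procedure before anyone is required to look at the cumulative data.

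The 7.6.1 rules do not fully close the gap. Of the six serious events of interest in 3.2.1, three do not appear there by name: exacerbation with a hospital stay over 24 hours, pneumonia within 7 days, and ventilation for more than 24 hours. They would halt the study only if judged an unanticipated adverse device effect (UADE). The population makes such events foreseeable: 6.1.5 requires an exacerbation in the prior year, and 10.2 rates infection and exacerbation as moderately likely.

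**Working it through.** The trigger of five is stated without a derivation, so there is no plan figure to reproduce. The check asks how far the trigger moves as halts and delays become more common.

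**Inputs from the documents**

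- Trigger: 5 completed second treatments (synopsis; 7.6.2).
- Maximum enrollment: 30 (8.2).
- Gap between procedures: 3 to 6 weeks, i.e. 21 to 42 days (7.2.4).
- Only figure near a non-completion rate: 25 right-side and 22 left-side procedures in the first-in-human study (1.3), so (25 − 22)/25 = 12% had no left-side treatment at the data cut. That study was ongoing and no reasons are given, so 12% is illustrative only.

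**Assumptions (not in the documents)**

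- Share halted, *h*, and share delayed, *r*, both as proportions of all treated subjects.
- Accrual of 2 or 4 first treatments per month.
- A delay of 28 days.

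**Step 1: subjects needed, ignoring calendar time.** The number of first-treated subjects that yields 5 completers is negative binomial with mean 5/(1 − *h*).

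| *h* | Mean, 5/(1 − *h*) | 90th percentile | P(more than 10 needed) |
|---|---|---|---|
| 0 | 5.0 | 5 | 0 |
| 0.12 | 5/0.88 = 5.7 | 7 | 0.04% |
| 0.2 | 5/0.8 = 6.3 | 8 | 0.6% |
| 0.3 | 5/0.7 = 7.1 | 9 | 4.7% |
| 0.5 | 5/0.5 = 10.0 | 14 | 37.7% |

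The chance that 30 subjects never produce 5 completers is below 0.01% up to *h* = 0.5 and 0.15% at *h* = 0.6. The issue is lateness, not loss of the review.

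**Step 2: calendar time.** The simulation used 20,000 runs, Poisson accrual and a gap uniform on 21 to 42 days. It counts subjects with a first procedure when the fifth second procedure is completed.

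| Halted / delayed | Mean at 2 per month | Mean at 4 per month (90th percentile) |
|---|---|---|
| 0 / 0 | 7.1 | 9.2 (12) |
| 12% / 0 | 7.8 | 9.8 (13) |
| 30% / 30% | 10.0 | 12.9 (17) |
| 40% / 30% | 11.3 | 14.3 (19) |

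Increase over no complications:

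- 12% / 0: 7.8 − 7.1 = 0.7; 9.8 − 9.2 = 0.6.
- 30% / 30%: 10.0 − 7.1 = 2.9; 12.9 − 9.2 = 3.7.
- 40% / 30%: 11.3 − 7.1 = 4.2; 14.3 − 9.2 = 5.1.

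**Step 3: the alternative trigger.** The count is instead taken when five treated subjects have a known Visit 4 outcome, at day 42 at the latest. Mean first-treated subjects then stay at 7.1 to 7.6 (2 per month) and 9.1 to 10.1 (4 per month) in all these scenarios. The price is fewer second procedures in that review: on average about 4.4 at 12% halted, 2.5 to 2.8 at 30% / 30%, and 2.0 to 2.3 at 40% / 30%. In the last case 5% to 8% of reviews would contain none.

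**The case against.** A reader might infer that this is the only formal safety review, and that every additional complication delays scrutiny. The documents do not support either reading. Section 7.6.1 imposes a halt and a mandatory review that does not depend on Visit 4, and 7.6.2 places the interim on top of those rules. A listed event brings review forward.

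The UADE rule could reach further than it first appears. The Definitions section counts a serious device-associated effect as unanticipated if its frequency was not foreseen. Section 10.2 puts infection and exacerbation at between 1 in 10 and 1 in 100, and respiratory failure, listed under anesthesia complications, below 1 in 100. Serious, device-associated events common enough to halt 30% to 40% of subjects could exceed those figures and stop the study. That point stands, with a limit: someone has to judge that the frequency is exceeded, which calls for a cumulative look that no schedule secures.

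Nor can one say that nobody would see cumulative data before the trigger. SAEs arrive within 24 hours and AEs are monitored; what is missing is a fixed time or criterion. Data from halted subjects are not ignored either, since they enter the review once it is held.

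The completer trigger also has a sound rationale: it guarantees some experience of both procedures. Simply replacing it would lose that, as step 3 shows. This objection stands and shapes the fix.

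Finally, the larger effects rest on assumed rates. At 12% halted with no delays the increase is under one subject.

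**Conclusion.** The concern holds in a limited form. The only scheduled aggregate safety review is timed by completed second treatments alone, with no fallback. Complications that halt or delay Visit 4 without meeting a stopping rule therefore postpone it while first procedures continue. The size depends on rates the documents do not give: about 0.7 extra first-treated subjects at 12% halted, 3 to 4 at 30% halted plus 30% delayed, and 4 to 5 at 40% halted plus 30% delayed, for accrual of 2 to 4 per month. The effect is small if complications are rare and grows in the situation an early safety review is meant to detect.

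No passages conflict over the trigger and no analysis is invalidated. It is a cheap improvement to a study whose primary objective is safety.

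**What to change.** In the synopsis and 7.6.2:

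1. Hold the interim review when five treated subjects have a known Visit 4 outcome: second treatment done, halted, or not done by the end of the Visit 4 window.
2. Report in that review how many of the five did not receive the second treatment, and why.
3. If it includes fewer than five second treatments, repeat it when five have been completed.

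The Visit 4 window must be reconciled first: 7.2.4 gives 3 to 6 weeks after the first bronchoscopy, while Table 7.1 prints a window of −3 to +6 weeks. The calculation above took day 42 as the end.

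The cost is a short wording change in two places and possibly one more meeting of the existing reviewers. At 12% halted and no delays, all five would have had the second treatment with probability about 0.88^5 = 0.53, so the repeat would be needed roughly half the time. The first review may contain materially fewer second procedures, which the repeat makes good. No treatment rule changes.

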1.0 INTRODUCTION

[figure not shown]
1.1 Background

Approximately 12 million patients in the United States, 13 million in the European Union and 4 million in Japan are diagnosed with Chronic Obstructive Pulmonary Disease (COPD) and millions more may have the disease without a diagnosis. COPD is the third leading cause of death in the United States. COPD causes serious long-term disability and early death. Currently, there is no cure for COPD and treatment aims simply to reduce exacerbations, reduce hospitalization and improve quality of life.

COPD severity is diagnosed by degree of FEV₁ reduction. FEV₁ is the volume of air exhaled by a patient in the first second when exhaling as hard as possible into a spirometer. Once diagnosed with COPD, drugs are prescribed based on standard guidelines (see Figure 1.1).

COPD is, however, most likely several different physiologic conditions that have been combined into one category. Most simply, emphysema and chronic bronchitis are two examples of subsets of COPD that vary physiologically.

Figure 1.1: COPD Severity and Interventions

Emphysema. Emphysema is a disease of the alveoli which are responsible for oxygen and carbon dioxide exchange. Inhaled toxins, from cigarette smoke in most cases, activate proteases leading to alveolar tissue destruction. As more alveoli are destroyed, patients cannot adequately oxygenate and carbon dioxide retention leads to chronic respiratory acidosis, which symptomatically manifests as shortness of breath.

Chronic Bronchitis. Chronic bronchitis is defined as the presence of cough with productive sputum for three months in duration for two consecutive years. It is a

disease of the airways, unlike emphysema which is a disease of the parenchyma (lung tissue) and alveoli. The pathophysiology of chronic bronchitis is not completely understood, but the leading theory extends from the British Hypothesis¹. Noxious gases and particles are introduced into the respiratory tract by inhalation of cigarette smoke, leading to innate and adaptive inflammatory responses of the airway mucosa. Over time, the chronic inflammation leads to abnormal tissue repair and remodeling of the bronchial walls, most notably with an increase in the number and size of the bronchial mucus glands, defective cilia, and disruption of the epithelial barrier². Abnormal, thick mucus is secreted into the airways that cannot easily be cleared and provides fertile ground for bacteria and other pathogens that would have otherwise been cleared. As more mucus accumulates in the airways, it obstructs air delivery to the alveoli resulting in decreased FEV₁³.

